**Protection of Human Subjects**

**Risks to the Subjects**

*Human Subjects Involvement and Characteristics.*

This protocol addresses 3 clinical research studies and a clinic-level study comparing system enhancements coming from modifications of the EHR to usual care Fax to Quit referral of smokers. The clinic level study has not human subjects. The 3 clinical research studies involve human subjects and that involvement is described below. For the clinic level study, necessary data for the intervention clinics will be obtained from the subjects in the clinical research as well as from the sample representativeness data described in Appendix 1 below. The additional data on non-study participants at the intervention clinics available through these aggregate sample representativeness data files will not include any identifiable private

“Breaking Addiction to Tobacco for Health (BREATHE) Study”

PI: [name], MPH, MBA; UW-CTRI Center Grant: 1P01CA180945-01.

information and these individuals are they not considered human subjects. All data from the control clinics (aggregate information on clinic visits and smoker rates obtained from the health systems and summary numeric data on the number of referrals received and served reported by the Wisconsin Tobacco Quitline for all fax referral sites) will be aggregate data with no identifiable private information. The patients participating in smoking cessation treatment as a result of their fax to quit/standard of care referral from the control clinics are therefore not considered human subjects and are not discussed further in this section of the protocol. In summary, the remainder of this human subjects section focuses on the human subjects who will participate in the clinical interventions as a result of referral from an active clinic assigned to the EHR intervention condition within the clinic randomized control trial, since these are the only human subjects involved in this set of studies.

Specific eligibility requirements for all 3 clinical studies within the intervention clinics are: 1) 18 years of age or older; 2) report smoking at least 5 cigarettes per day for the previous 6 months; 4) able to read and write English; 5) have reliable phone access and agree to respond to Interactive Voice Response (IVR) phone prompts 8) free of medical contraindications to NRT; and 9), if participant is a woman of childbearing potential, using an approved method of birth control during treatment. Participants who are eliminated due to screening failure, or elect not to participate in this research medication program, will be given a list of alternative smoking cessation programs, including an opportunity to receive usual care from the clinic and a referral to the Wisconsin Tobacco Quit Line ([name]). For the Motivation Study, participants also have to be not currently attempting to quit smoking or intending to quit smoking (defined as no plans to quit in the next month); and planning to remain in the intervention catchment area for at least 12 months. For the Cessation Study, participants also have to be motivated to quit smoking and planning to remain in the intervention catchment area for at least 12 months. For the Long-term Quitting Study, participants also have to be motivated to quit smoking and planning to remain in the intervention catchment area for at least 2 years and 2 months.

A minimum of 2112 participants will be recruited to participate in this research: 512 in the Motivation Study, 600 in the Cessation Study and 1000 in the Long-term Quitting Study. However, to get a proper balance of participants across the three studies, we may recruit as many as 2600. No special vulnerable populations will be intentionally recruited (pregnant women will be specifically screened out due to medication safety concerns and no persons under the age of 18 will be allowed to participate because the medications we are using have not been approved by the FDA for individuals less than 18 years old). See the Inclusion/ Exclusion section for protocol regarding participants previously eligible who become incarcerated or pregnant.

Eligible participants will be randomized at the point of screen passing the phone screen (stratified by gender). Those who do not enroll will be unrandomized and the treatment condition assigned to them will be reassigned to a new preparticipant.

Medication dosing will be consistent with the 2008 PHS Guideline, other recent clinical practice guidelines, and package inserts (smoke within 30 min of waking = 4-mg mini-lozenge; smoke more than 30 min after waking = 2-mg mini-lozenge; smoke >10 cigs/day = start with 21-mg patch; smoke <=10 cigs/day = start with 14-mg patch). Starting Spring 2018 we started to screen individuals who would be prescribed mini-lozenges for soy allergens prior to dissemination to prevent allergic reaction AEs - per the ML new package insert. Research

“Breaking Addiction to Tobacco for Health (BREATHE) Study”

PI: [name], MPH, MBA; UW-CTRI Center Grant: 1P01CA180945-01.

personnel will recommend dosage/use alterations as per good clinical practice if the participant experiences symptoms of nicotine toxicity or side effects. The health counselor will refer participants to their primary care physician should they require medical consultation. Medication is provided to participants in dosage periods defined within each protocol. It is important to note that study medication use in this research is all in accordance with FDA guidelines, including using NRT for longer than 8 weeks, before quitting, and in combinations (e.g., patch + mini-lozenge). For the Motivation and Long Term Quitting studies, if a medication is discontinued due to one or many NRT symptoms, or the patient had a CVD event in the last 4 weeks, that medication will not be prescribed at a later phase. No further medications will be given to this study participant while in the study.

The research involves collaborating sites at Penn State University and University of Illinois-Chicago. Neither of these sites will collect data. Investigators at these two sites will work with cleaned, limited analytic data sets provided by UW-CTRI through secure web access to the named investigators. The work of both sites will be overseen by their own institutional IRB's. The data sets provided by UW-CTRI will conform to the rules for a limited data set, including dates of service and an identifier that allows for analysis at the individual study participant level. The research also involves collaboration with staff of two health systems (Aurora Health Care and Dean Health). In prior research of similar scope, their involvement has been determined to be not involved in research since their role is limited to providing information about the availability of a study and sending contact information to the study staff, as well as providing other types of aggregate data. No identifiable research data from UW-CTRI are shared with the clinics.

*Sources of Materials.* Data on those expressing interest in the study within their healthcare clinic are gathered by electronic health record (EHR). This statement of interest generates an electronic transmission of the person's contact information (address and phone) to a password-protected email account accessed by specifically named study personnel. The contact information is entered into the study database.

Data collected from participants in this Program Project will primarily be used for research. Data will consist of answers to questionnaires, automated phone assessments, and interviews assessing smoking history, demographics, nicotine dependence, personality, affect, and breath samples to permit determination of carbon monoxide. Carbon monoxide assays reflect smoking status. All data are retained in the study database. The study database access is limited to those staff members and investigators directly involved in the study and under the supervision of the UW IRB.

*Potential Risks.* Risks associated with this research are judged to be minimal. Smoking withdrawal is associated with a number of unpleasant symptoms such as sleep disturbance, hunger, craving, and negative mood. Most smokers have tried to quit in the past and are familiar with these phenomena. Participants will be informed about the likely effects of smoking withdrawal.

With respect to the pharmacotherapies, participants will be made aware of the common side effects before they consent to participate in the study. It should be noted that the nicotine mini-lozenge and patch are available over the counter. The nicotine patch is generally well tolerated, but up to 50% of participants may have a local skin reaction, and rarely, individuals

“Breaking Addiction to Tobacco for Health (BREATHE) Study”

PI: [name], MPH, MBA; UW-CTRI Center Grant: 1P01CA180945-01.

may have a more systemic allergic reaction. The most likely side effects associated with the nicotine mini-lozenge are heartburn, nausea, hiccups, and sore throat. Although most smokers have tolerance to nicotine, symptoms of acute nicotine toxicity (nausea and vomiting) are possible. The two other primary FDA approved alternative medication treatments for smoking cessation are bupropion and varenicline. Both have a considerably greater side effect profile than nicotine replacement products and require extensive medical monitoring. Finally, individuals often attempt to stop smoking without the use of medication. As the 2008 PHS Guideline shows, this method is considerably less likely to produce long-term cessation. Those not successful in quitting bear the health risks associated with continued smoking.

Finally, there is a small risk of loss of confidentiality. This could occur through a number of possible avenues, all highly unlikely due to the data security measures in place. UW-CTRI's computer system is linked to the UW network through a firewall, which is managed by the School of Medicine and Public Health network team, via a fiber link which is maintained by the UW Division of Information Technology. No data are stored on individual computer hard drives. All data are transmitted from the point of collection to the UW-CTRI server through secure, encrypted web connection. There are rare occasions when, due to a loss of internet access or computer hardware failure, data are collected in paper forms, which could be taken or lost. In addition, consent forms are obtained in paper copy; these forms contain the participant name and signature. Finally, the University of Wisconsin and the National Cancer Institute may inspect the signed consent forms. Because of this possible need to release information to these parties, we cannot guarantee absolute confidentiality.

Adequacy of Protection Against Risks

*Recruitment and Informed Consent.* To ensure that our findings are maximally relevant to real-world healthcare application, we will screen smokers presenting to 18 primary care clinics (PCCs) in two participating health systems located throughout Southern Wisconsin. Participants will be recruited via two methods. 1) Participants will be recruited by the clinic's roomers (e.g., Medical Assistants) with methods similar to methods used in our prior research. Prompted by the electronic health record (EHR), roomers will screen all patients for smoking status and then will ask all smokers if they are interested in learning about treatments to help them quit now or in the future or reduce their smoking. They will also describe standard of care services their clinic has available. If the patient is interested, a one-click referral will send an EHR-generated Smoker Interest Form, containing patient contact information, to the research office. The roomer will also flag the patient's chart so that the physician will know that the patient's smoking has already been addressed and will not offer a smoking cessation intervention or study participation in the upcoming clinical encounter. 2) In the second recruitment method, smokers at participating clinics will receive direct recruitment information via mailings and EHR-specific messaging as part of the Smoker Registry. The direct recruitment messages will encourage smokers to learn more about the study by either providing their contact information so the study can contact them or by calling the research office directly.

The EHR-generated messages about interested patients or telephone messages left by interested patients will prompt a screening call from our research personnel within 48-72 hours to introduce the study options, assess interest and screen for eligibility. If the person is interested in one of the studies and is eligible, an in-person appointment at their referring clinic with a study staff member is set up. At this visit, the smoker will learn about general requirements for participation (e.g., need for follow-up, participation in assessments) as well as

“Breaking Addiction to Tobacco for Health (BREATHE) Study”

PI: [name], MPH, MBA; UW-CTRI Center Grant: 1P01CA180945-01.

risks associated with nicotine toxicity, nicotine withdrawal, and the pharmacotherapies. The health counselor will then provide each study candidate with an IRB-approved informed consent document corresponding with the study which they have chosen. Study candidates will read the informed consent document and be given an opportunity to ask any questions regarding study participation. A research staff member will read the consent form to the study candidate if needed or desired. The consent form will include necessary HIPAA language. Participants will be required to sign the consent form. Case managers will provide participants with a copy of the consent form.

*Protection Against Risk.* Risks related to medications are minimized through close monitoring. The leader for each study (Project Leaders), working in consultation with the Program Project’s physician ([name]), will be responsible for routine monitoring of unanticipated health events. This risk protection includes procedures for contacting the emergency physician or psychologist and monitoring of all events through scheduled biweekly meetings with study staff and review of written documentation. Unanticipated health event assessment, recording, reporting and investigation will be accomplished through staff training, structured/standardized assessments of untoward occurrences/events, and regular monitoring by study physicians and other study investigators. The Project Leaders and the Program Project Co-Principal Investigators have ultimate responsibility for ensuring that unanticipated health events are detected and reported in a timely manner. Health events that raise concerns (e.g., allergic reaction, symptoms suggestive of nicotine toxicity, significant change in mood, suicidal ideation) will be immediately reported to the study physician who will determine an appropriate course of action.

To facilitate safety, participants who may not be medically appropriate to take NRT will not be included in the study (e.g., hospitalized within the past month for a stroke, heart attack, congestive heart failure or diabetes). Once enrolled, follow-up protocols will assess for medication side effects and unanticipated health events at all study visits and follow-up contacts. We will recommend NRT dosage/use alterations as per good clinical practice if the patient experiences symptoms of nicotine toxicity or other troublesome side effects once they begin medication treatment. We will refer participants to their referring physician as needed. Should either excessive risk to study participants and/or lack of measurable benefit to study participants be determined, the study will be stopped and all participants notified in a manner appropriate to the nature of the risk and/or lack of benefit.

In terms of confidentiality risk, the UW-CTRI Information Technology Administrator manages the hardware, data, security, and infrastructure below the firewall. Access to the network is limited to only UW-CTRI owned and actively managed devices. All devices automatically lock and are password protected after 15 minutes of inactivity. All portable devices are encrypted for data security and no PHI is stored on local devices. All data stored on the network file server is limited by the principle of least privilege.

As stated above, no data are stored on individual computer hard drives. All data are transmitted from the point of collection to the UW-CTRI server through secure, encrypted web connection. On those rare occasions when, due to a loss of internet access or computer hardware failure, data are collected in paper forms, these forms will be stored securely in the clinic and transported personally by the case manager to UW-CTRI. No identifying data other than a participant ID number is entered on any data form. Any paper collected data are entered

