**Inclusion/Exclusion**

Inclusion criteria for all 3 studies will be: age (18 years or older); smoking >4 cigarettes/day for the previous 6 months; able to read, write, and speak English; have reliable phone access and agree to respond to Interactive Voice Response (IVR) phone prompts; a patient at a clinic currently recruiting in the study; not currently taking bupropion; if currently using nicotine replacement therapy (NRT) or varenicline, agreeing to use only study medication for the duration of the study; free of medical contraindications to using NRT; no history of stroke, mini-stroke, heart attack, TIA (Transient Ischemic Attack) nor an abnormal electrocardiogram in the past 4 weeks; no hospitalizations for diabetes or congestive heart failure in the past 4 weeks; no diagnosis of or treatment for schizophrenia, a psychotic disorder or bipolar disorder in the last 10 years; and, if the participant is a woman of childbearing potential, using an approved method of birth control during treatment. We will not exclude participants based on their prior use of cessation medication or if they use multiple tobacco products in order to enhance real-world generalization (these will be statistically controlled in analyses). However, we will encourage participants to discontinue use of all tobacco products on their target quit date.

Additional inclusion criteria for the individual studies include:

- Motivation Study: not currently attempting to quit smoking; not intending to quit smoking (defined as no plans to quit in the next month); and planning to remain in the area for at least 12 months.
- Cessation Study: reporting being motivated to quit; and planning to remain in the area for at least 12 months.
- Long-term Quitting Study: reporting being motivated to quit; and planning to remain in the area for at least 2 years and 2 months.

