**Motivation Study**

*Primary Aim 1: Determining the main and interactive effects of the intervention components on primary outcomes.* Our primary outcomes, assessed at both 6 months (end of treatment) and 12 months, are: 1) making a serious quit attempt (defined as  $\geq 48$  hours of nonsmoking as part of an intentional effort to quit); and 2) cessation success (defined as 7-day point-prevalence abstinence (PPA)—self-reported abstinence from smoking, even a single puff). With each of the components, we hypothesize that the "on" condition will produce higher quit attempts and cessation success than the "off" condition. Data for these aims come from phone assessments over the 12 months. We will model abstinence longitudinally via a mixed-effects logistic regression model including the main effects of treatment. Longitudinal models will include the effects of time, condition, and a random subject effect to account for the correlation of repeated assessments within subjects. We will also identify any interaction effects that emerge from the combinations of intervention components. For example, we will examine whether the combination of the BR and 5Rs has a larger or smaller effect than their additive

“Breaking Addiction to Tobacco for Health (BREATHE) Study”

PI: [name], MPH, MBA; UW-CTRI Center Grant: 1P01CA180945-01.

effects would predict. Although we will examine all possible interactions of the intervention components, we do not anticipate significant effects beyond 2-way interactions. *In sum, the proposed analyses will determine whether the tested intervention components, either via main or interaction effects, increase meaningful quit attempts and long-term abstinence rates.* In addition, we will use logistic regression analyses with effects-coding to examine the effect of each intervention component on the occurrence of the binary outcomes of quit attempt occurrence and PPA at different follow-up points. Models will include only main effects and two-way interactions; no higher-order interactions are expected. Following the intent-to-treat principle, all 512 participants randomized to treatment will be included; missingness will be investigated in other analysis

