*Secondary Aim 1: Determining the main and interactive effects on secondary outcomes.* We will use generalized linear mixed models to test main and interactive effects of components on smoking reduction. Entry into Cost-Optimized cessation treatment will be analyzed via logistic regression models that include main effects and two-way interactions. Cost for each treatment component will be tracked and used to identify optimal intervention components for further study and to aid decision making.

*Secondary Aim 2: Mediation analyses.* We will use a Bayesian multi-mediator approach, with the longitudinal data collected during the automated phone assessments to examine whether quit attempts and cessation success are predicted by treatment effects on key putative mediators: craving, self-efficacy, number of cigarettes smoked per day, tobacco dependence, intrinsic motivation, anhedonia, medication use, and contextual restrictions of smoking. Multi-mediator models will comprise mediators that are significant in univariate mediation analyses and allow us to address questions such as whether BR Counseling, relative to no BR, increases strength of participants’ self-efficacy, their use of reduction skills, or their magnitude of smoking reduction, and whether these increases result in increased quit attempts, and/or cessation rates. Or, does assignment to the Nicotine Mini-Lozenge condition, relative to assignment to No Nicotine Mini-Lozenge, increase participants’ self-efficacy, or decrease their craving, or amount of smoking reduction, and do these changes result in increased quit attempts, and/or cessation rates?

*Secondary Aim 3: Moderation analyses.* Potential moderators (e.g., age, gender, dependence) will be tested in moderated logistic regression models. These models will include main effects for all treatments and the moderator (e.g., gender) as well as two-way interactions of each treatment effect and the moderator.

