**Cessation Study**

*Primary Aim 1:* A primary aim of Project 3 is to compare Abstinence-Optimized Cessation Treatment (AOCT) with Modern Usual Care (M-UC) on 7-day point-prevalence abstinence evaluated at 8, 16, 26, 39 and 52 weeks postquit. We will use GLMM implemented via SAS PROC GLIMMIX (SAS Institute Inc., Cary, North Carolina) to test the group effects in longitudinal models. Specifically, we hypothesize that participants receiving AOCT will have higher cessation rates at each timepoint than those receiving M-UC. We will also analyze other clinical outcomes because they provide complementary information about outcome (e.g., initial cessation, 6- and 12- month point-prevalence abstinence, latency to lapse and relapse, and treatment engagement and adherence) as recommended by SRNT Workgroup and others. We will evaluate initial cessation (did or did not establish 24 hours of abstinence in the first 2 weeks

“Breaking Addiction to Tobacco for Health (BREATHE) Study”

PI: [name], MPH, MBA; UW-CTRI Center Grant: 1P01CA180945-01.

following the quit day) and 6- and 12-month abstinence rates using logistic regression and latency to lapse and relapse using Cox proportional-hazards regression. We will also examine cessation outcomes controlling for treatment adherence in secondary analyses. The distributions of the adherence data (percentage of days using nicotine replacement; number of mini-lozenges used per day; percentage of counseling sessions completed) will be examined to inform decisions about transformation and analysis options.

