***Long-term Quitting Study***

The analytic plan reflects that the treatments will be delivered in sequence (i.e., analyses will accommodate the transition of participants across the RR Preparation and RR Cessation treatments) as is recommended for SMART designs.

*Primary Aim.* To determine the effects of the RR Preparation treatment on abstinence at the Month 14 Preparation assessment time point amongst participants randomized to RR Preparation treatment (“active” and “control”). This analysis will be conducted using generalized linear models (GLM) with point-prevalence abstinence data as the outcome variable. Potential covariates will include: race, gender, tobacco dependence (e.g., before initial cessation treatment) and duration of abstinence in the initial cessation attempt. The main model will not control for RR Cessation factors; rather it will focus on the question of whether long-term differences in abstinence rates emerge from the RR Preparation treatment. These analyses will be done in several ways: 1) by comparing each active RR Preparation component with the Preparation Control condition, and 2) by conducting a GLM analysis comprising only the RR Reduction vs. Recycling Preparation participants. The former will address the issue of whether the active Preparation components, and any consequential access to RR Cessation treatment, affects the long-term smoking outcomes of participants. Results will be examined to determine the extent to which differences are related to the use of RR Cessation treatments. The second type of analysis will focus on the active RR Preparation components, when participants in each component have an equal chance of being assigned to any of the RR Cessation intervention components. RR Cessation factors will be used as covariates in supplementary analyses of the active components and the interactions of these factors with Preparation treatment condition will be examined. Marginal frequencies will be examined to determine the rate at which participants elect to be randomized to RR Cessation treatment.

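### The Motivation and Cessation primary models omit gender, which stratifies randomisation, and the covariates the protocol says it will control; the tests stay valid, but a little power and a prespecified estimate are given up.

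*Combined protocol and SAP*

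**What the plan says.** **Randomisation.** Protection of Human Subjects, Risks to the Subjects, covers all three clinical studies: "Eligible participants will be randomized at the point of screen passing the phone screen (stratified by gender"). Gender is the only stratifier named there.

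**Promised control.** Inclusion/Exclusion admits smokers whatever their prior use of cessation medication, and admits users of several tobacco products. It adds in parentheses that "these will be statistically controlled in analyses". It does not say which analyses.

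**Motivation Study, Analytic Plans.** "Longitudinal models will include the effects of time, condition, and a random subject effect". For the logistic models at separate follow-up points: "Models will include only main effects and two-way interactions; no higher-order interactions are expected". Gender enters only under Secondary Aim 3: "Potential moderators (e.g., age, gender, dependence) will be tested in moderated logistic regression models".

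**Cessation Study, Analytic Plans.** "We will use GLMM implemented via SAS PROC GLIMMIX", and the purpose given is "to test the group effects in longitudinal models". No covariate is named for Primary Aim 1. Gender and baseline dependence appear only as possible moderators in exploratory analyses.

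**Long-term Quitting Study, Analytic Plans.** The primary aim is handled differently: "Potential covariates will include: race, gender, tobacco dependence", together with duration of abstinence in the first quit attempt.

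**The concern.** A factor used to balance the arms is normally carried into the primary model, and baseline variables that a protocol says it will control should appear in the models where the control is to happen. Neither is done here for two of the three studies. The sister study does list such covariates, so the gap does not look like a deliberate policy of unadjusted analysis.

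Two things are at stake. The first is power that costs no extra participants, in studies whose stated single-endpoint power is only .80 and .81. The second is prespecification. In a logistic model the adjusted and unadjusted odds ratios are different quantities. With a general promise of control in one section and models without covariates in another, the choice between them could be made after the data are seen.

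**Working it through.** **1. Reproduce the plan's own power.** Two-sided alpha .05 (sidedness is not stated for these calculations, so this is assumed), pooled variance under the null, no continuity correction:

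power = Φ[(d − 1.96·SE0)/SE1], with SE0 = √(2·p̄(1−p̄)/n) and SE1 = √((p1(1−p1)+p2(1−p2))/n).

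- Cessation, 6-month abstinence, 20% vs 30%, n = 300 per arm. SE0 = √(2·.25·.75/300) = .0354; SE1 = √((.16+.21)/300) = .0351; (.10 − .0693)/.0351 = .874. Power .809, stated .80.
- Motivation, quit attempts, 60% vs 72%, n = 256 per level. SE0 = √(2·.66·.34/256) = .0419; SE1 = √((.24+.2016)/256) = .0415; (.12 − .0821)/.0415 = .913. Power .819, stated .81.

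Both reproduce without adjustment. With a continuity correction they are .782 and .794.

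**2. Power with covariates added.** This was simulated: single-endpoint logistic regression, treatment balanced within gender, marginal rates held at the protocol's values, 4,000 trials per scenario. Differences below about 0.3 points are within simulation noise. All prognostic strengths are assumptions.

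*Gender alone*, assumed odds ratio 1.0 to 2.0. Figures at 2.0, the largest value tried:

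| Comparison | Treatment only | Plus gender | Gain (points) |
|---|---|---|---|
| Cessation 20% vs 30% | .809 | .813 | 0.4 |
| Motivation quit attempts 60% vs 72% | .813 | .821 | 0.8 |
| Motivation abstinence 10% vs 18%, one time point | .741 | .750 | 0.9 |

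*Gender (odds ratio 1.25) plus one standardised baseline covariate*, by assumed odds ratio per SD:

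| Comparison | 1.35 | 1.65 | 2.23 |
|---|---|---|---|
| Cessation 20% vs 30% | .812 to .818 (+0.6) | .808 to .827 (+1.9) | .808 to .845 (+3.7) |
| Motivation quit attempts | .808 to .820 (+1.2) | .814 to .842 (+2.9) | .820 to .861 (+4.1) |
| Motivation abstinence | .746 to .752 (+0.6) | .748 to .765 (+1.7) | .746 to .779 (+3.3) |

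**3. Where the gain comes from.** For 20% vs 30% with 300 per arm, the unadjusted standard error of the log odds ratio is √(1/(300·.2·.8) + 1/(300·.3·.7)) = √(1/48 + 1/63) = .192. In simulation it rises with the covariate in the model, to about .194, .197 and .204 at the three assumed strengths. Power still improves because the conditional log odds ratio is larger by more than the standard error grows.

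**4. Validity of the unadjusted test.** With 20% in both arms and 10,000 trials per scenario, type I error of the treatment-only model was 4.6% to 5.0%.

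**5. Is a clinic term workable?** The protocol recruits from about 18 clinics. Assuming an equal split, 512/18 is about 28 Motivation participants per clinic. At 10% abstinence that is about 2.8 events. The chance of no event in a clinic is .9^28 = .052, so the chance that at least one of 18 has none is 1 − .948^18, about 62%. Fixed clinic effects would risk separation.

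**6. Are the covariates available at baseline?** Tobacco dependence is in the standard Visit 1 assessment for all studies. In Table 11 (Motivation) the Dual Use row starts at Week 12. Tobacco use history and current tobacco use are marked at Visit 1 and may supply the item, but the protocol does not say so.

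**The case against.** The best defence is that the sections can be read together. Inclusion/Exclusion makes a general commitment; the Cessation text names a procedure and a test but gives no closed list of terms; and the Motivation sentence limiting the logistic models to main effects and two-way interactions may concern interaction order, not covariates. This has force. A reader might infer a flat self-contradiction, but the documents show only that the promise is not carried into the two primary models. For Cessation the plan is silent, not exclusive. The silence still leaves the primary estimate undefined.

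The defence also says that the numerical stake is small, and for gender that is right.

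Three stronger readings are tempting and fail:

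- *The unadjusted tests are invalid, or the stated powers are wrong.* Type I error is intact, and .80 and .81 reproduce.
- *Adjustment shrinks the standard error in proportion to the variance explained.* Scaling the variance by (1 − R²) with R² of 2% to 15% would lift Cessation power from .81 to between .82 and .87. That is linear-model reasoning. In the logistic models checked here the standard error rises, and the documents supply no R².
- *Clinic is a stratifier that has been dropped.* Participants come from about 18 clinics, but no section stratifies individual randomisation by clinic.

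**Conclusion.** The omission stands: neither primary model names gender or the two covariates that the protocol undertakes to control. Its consequence is modest: under 1 power point for gender, and about 0.6 to 4 points for gender with one prognostic baseline covariate across the assumed range. If the baseline variables turn out weakly prognostic, the gain is close to nothing. The case for acting rests at least as much on fixing the estimate in advance.

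The power gains come from single-endpoint logistic models, which both studies also plan to use. They only approximate the longitudinal mixed models. There the random subject effect already makes the odds ratio subject-specific, so the gain may divide differently between estimate and standard error. The stated longitudinal powers (.91 for Cessation; .94 and .99 for Motivation) depend on details of the sample-size macro and are not relied on here.

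**What to change.** For both primary models, and for the accompanying single-time-point logistic models, state that gender, baseline tobacco dependence, prior cessation-medication use and multiple-product use enter as fixed covariates, and give the coding of each. Name the adjusted conditional odds ratio as the primary estimate and report the unadjusted result as a check. In the Motivation section, reword the sentence on main effects and two-way interactions so that it plainly refers to treatment terms.

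Use only baseline values that treatment cannot have influenced. Allocation is made when the phone screen is passed, so Visit 1 items are collected after it. The plan should confirm that the items used are recorded before the participant learns the assignment or starts treatment. For Motivation, confirm which Visit 1 item supplies multiple-product use; a Week 12 value must not be used.

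Fixed clinic effects should not be required.

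The cost is a few sentences in the analysis plan and a check of the Visit 1 forms. Sample size and visit schedule do not change. If no Visit 1 item covers multiple-product use in Motivation, that covariate is either left out of that model with a stated reason or needs one added baseline question, if enrolment is still open.
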